5. Have at least one brain metastasis that is at least 5 mm AND twice the MRI slice thickness, but less than or equal to 3 cm, which is asymptomatic, has not been previously radiated, and is not requiring immediate local therapy or steroids. Lesions situated in a previously irradiated area are considered allowed if measurable per the aforementioned criteria and if progression has been demonstrated. Patients with any lesion(s) >3 cm can be enrolled provided the following: (1) the lesion must receive local treatment prior to initiation of study drugs (either by stereotactic radiosurgery or resection), (2) the patient is not symptomatic from the lesion(s) once local therapy has been administered, and (3) at least one additional, non-treated lesion between 5 mm and 3 cm is still present.
6. Prior treatment for either the Melanoma or RCC cohorts may include:
Patients must have received at least 2 doses of an anti-PD-1/PD-L1 drug at some point in their treatment course. Any number of prior treatments including PD-1/PD-L1 inhibitors are allowed. Anti-PD-1/PD-L1 does not have to be the most recent therapy. Patients with melanoma who developed brain metastasis within 6 months of the last dose of adjuvant anti-PD-1 can be enrolled.
7. Life expectancy of at least 3 months.
8. A history of radiotherapy for brain metastases is allowed up to 1 week before study treatment provided that neurologic sequelae are resolved, and that measurable untreated target lesion(s) remain.
9. Have an Eastern Cooperative Oncology Group (ECOG) performance status of 0 to 1. Evaluation of ECOG is to be performed within 7 days prior to the date of allocation.
10. Adequately controlled blood pressure (BP) with or without antihypertensive medications, defined as a systolic BP ≤ 150 or a diastolic BP ≤ 90 mmHg at screening and on Cycle 1 Day 1.

Note: Eligibility of a participant that is receiving ≥ 3 antihypertensive medications prior to study entry will require PI approval.
11. Have adequate organ function as defined in the following table (Table 1). Specimens must be collected within 10 days prior to the start of study treatment.

12. Table 1 Adequate Organ Function Laboratory Values

System	Laboratory Value
Hematological	
Absolute neutrophil count (ANC)	$\geq 1500/\mu\text{L}$
Platelets	$\geq 100\,000/\mu\text{L}$
Hemoglobin	$\geq 9.0\text{ g/dL}$ or $\geq 5.6\text{ mmol/L}^a$
Renal	

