22. Has urine protein ≥ 2 g/24-hour.

Note: Participants with $>1+$ proteinuria on urine dipstick will undergo 24-hour urine collection for quantitative assessment of proteinuria.
23. Evidence of a bleeding diathesis, risk for severe hemorrhage, or clinically significant coagulopathy.
24. Uncontrolled hypertension (systolic BP >150 mmHg or diastolic BP >90 mmHg) in spite of an optimized regimen of antihypertensive medication.

25. Has a history of (non-infectious, non-radiation-induced) pneumonitis not responsive to steroids or has current pneumonitis. Patients will also be excluded if there are respiratory issues including active infection or require supplemental oxygen for activities of daily living.
26. Has an active infection requiring systemic therapy.
27. Has a known history of Human Immunodeficiency Virus (HIV).
28. Has a known history of Hepatitis B or known active Hepatitis C virus infection.

Note: No testing for Hepatitis B and Hepatitis C is required unless mandated by local health authority.

29. Has a history or current evidence of any condition, therapy, or laboratory abnormality that might confound the results of the study, interfere with the subject's participation for the full duration of the study, or is not in the best interest of the subject to participate, in the opinion of the treating investigator.
30. Has known psychiatric or substance abuse disorders that would interfere with cooperation with the requirements of the trial.
31. Is pregnant or breastfeeding or expecting to conceive or father children within the projected duration of the study, starting with the screening visit through 120 days after the last dose of trial treatment.
32. Women of child-bearing potential who are unwilling to or unable to use an acceptable method of contraception to avoid pregnancy for the entire study and for at least 5 months after cessation of study drug or have a positive pregnancy test at screening or baseline, or who are pregnant or breast feeding.

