5.2.2.4 Management of AEs associated with lenvatinib

Lenvatinib dose reduction and interruption for participants who experience lenvatinib- related toxicity that are not considered irAEs will be in accordance with the dose modification guidelines described in Table 5. An interruption of study treatment for more than 28 days will require PI consultation and approval before treatment can be resumed.

Adverse events will be graded using NCI CTCAE v5.0. For presumed non irAEs, investigators will decide the probability of the event being related to lenvatinib and whether dose modification or interruption/discontinuation, as applicable, of one or both drugs is required. The starting dose of lenvatinib is 20 mg/day for participants enrolled. Dose reductions of lenvatinib occur in succession based on the previous dose level (14, 10, and 8 mg/day). Any dose reduction below 8 mg/day must be discussed with the PI. Once the study drug dose has been reduced, it may not be increased at a later date, unless the dose was mistakenly decreased; in this situation, PI's approval is required to increase the dose.

Refer to the subsections below for management of hypertension (Section 5.2.2.6), proteinuria (Section 5.2.2.7), diarrhea (Section 5.2.2.8), hepatotoxicity (Section 5.2.2.9), thromboembolic events (Section 5.2.2.10), posterior reversible encephalopathy syndrome/reversible posterior leukoencephalopathy syndrome (PRES/RPLS; Section 5.2.2.11), hypocalcemia (Section 5.2.2.12), and hemorrhage (Section 5.2.2.13), as appropriate, before consulting the dose modification table (Table 5).

- BP should be well-controlled prior to the start of lenvatinib. Blood pressure should be monitored after 1 week of treatment with lenvatinib, then every 2 weeks for the first 2 months and at the beginning of each cycle thereafter while on treatment. If a patient develops systolic BP ≥ 150 mmHg or diastolic BP ≥ 90 mmHg active management is indicated.
- Urine protein should be monitored regularly. If urine dipstick $\geq 2+$ is detected, dose interruptions, adjustments, or discontinuation may be necessary. Discontinue in the event of nephrotic syndrome.
- Monitor and correct all electrolyte abnormalities in all patients.
- Liver function tests should be monitored before initiation of treatment, then every 2 weeks for the first 2 months and monthly thereafter during treatment. In the case of hepatotoxicity, dose interruptions, adjustments, or discontinuation may be necessary.

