5.2.2.6 Management of Hypertension

Hypertension is a recognized side effect of treatment with drugs inhibiting VEGF signaling. Investigators should therefore ensure that participants enrolled to receive treatment with lenvatinib have BP of $\leq 150/90$ mm Hg at the time of study entry and, if known to be hypertensive, have been on a stable dose of antihypertensive therapy for at least 1 week before Cycle 1 Day 1. Early detection and effective management of hypertension are important to minimize the need for lenvatinib dose interruptions and reductions.

Regular assessment of BP should be as detailed in the Study Flow Chart (Section 6.1). Hypertension will be graded using NCI CTCAE v5.0, based on BP measurements only (and not on the number of antihypertensive medications). If the participant's initial BP measurement is elevated (ie, systolic BP ≥ 140 mm Hg or diastolic BP ≥ 90 mm Hg), the BP measurement should be repeated at least 5 minutes later.

One BP assessment is defined as the mean value of 2 measurements at least 5 minutes apart. If the BP assessment (ie, the mean of the 2 BP measurements obtained at least 5 minutes apart) is elevated (systolic BP ≥ 140 mm Hg or diastolic BP ≥ 90 mm Hg), a confirmatory assessment should be obtained at least 30 minutes later by performing 2 measurements (at least 5 minutes apart) to yield a mean value.

Antihypertensive agents should be started as soon as elevated BP (systolic BP ≥ 140 mm Hg or diastolic BP ≥ 90 mm Hg) is confirmed on 2 assessments at least 30 minutes apart. The choice of antihypertensive treatment should be individualized to the participant's clinical circumstances and follow standard medical practice. For previously normotensive participants, appropriate antihypertensive therapy should be started when systolic BP ≥ 140 mm Hg or diastolic BP ≥ 90 mm Hg is first observed on 2 assessments at least 30 minutes apart. For those participants already on antihypertensive medication, treatment modification may be necessary if hypertension persists.

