6.0 TRIAL FLOW CHART

6.1 Study Flow Chart

Trial Period:		Treatment Cycles ^a								EOT ^b	Post-Treatment			Notes
Treatment Cycle/Title:	Main Study Screening Visit	1	2	3	4	To be repeated beyond 8 cycles				Discon	Safety FU ^{b,c}	FU Visits	Survival Follow-Up	
						5	6	7	8					
Scheduling Window (Days):	-28 to -1		± 3	± 3	± 3	± 3	± 3	± 3	± 3	At time of Discon	30 and 90 days post discon	Every 12 weeks post discon	Every 12 weeks	
Administrative Procedures														
Informed Consent	X													Consent form can be signed at any time prior to any protocol-specific screening procedures being performed. Additional consent is required at initial disease progression per RECIST 1.1.
Inclusion/Exclusion Criteria	X													
Demographics and Medical/Surgical History	X													Significant medical/surgical history will be captured for last 10 years.
Prior and Concomitant Medication Review	X	X	X	X	X	X	X	X	X	X	X	X		Concomitant medications will be recorded for 90d after last dose (or for up to 120d after last dose for SAEs).
Pembrolizumab and Lenvatinib Administration		X	X	X	X	X	X	X	X					Pembrolizumab 200 mg Q3W with lenvatinib 20 mg QD; 21-d cycle
Post-study anticancer therapy status											X	X	X	All anticancer therapy will be recorded until time of death or termination of survival follow-up. If a clinic visit is not feasible, follow up information may be obtained via telephone or email.
Survival Status		X	X	X	X	X	X	X	X	X	X	X	X	
Clinical Procedures/Assessments														

Review Adverse Events		X	X	X	X	X	X	X	X	X	X			AEs: monitored up to 90d after last dose. SAEs and pregnancy: monitored up to 120d after last dose, or 30d after last dose if participant starts a new anticancer therapy, whichever is sooner
Full Physical Examination	X													To be performed within 7d of C1D1.
Directed Physical Examination		X	X	X	X	X	X	X	X	X	X	X	X	
Vital Signs and Weight ^d	X	X	X	X	X	X	X	X	X	X				BP and HR will be measured after the participant has been resting for 5 minutes. See Section 5.2.2.6 for management of hypertension and Section 7.1.2.4 for vital signs. Height is measured at Screening only.
ECOG Performance Status	X	X	X	X	X	X	X	X	X	X				
12-lead ECG	X													Single 12-lead ECG. Participants must be in the recumbent position for a period of 5 minutes prior to the ECG. Additional assessments may be performed if clinically indicated.
Laboratory Procedures/Assessments: analysis performed by LOCAL Lab ^g														

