7.1.2.4 Vital Signs

The investigator or qualified designee will take vital signs at screening, prior to the administration of each dose of trial treatment and at treatment discontinuation as specified in the Trial Flow Chart (Section 6.0). Vital signs should include temperature, pulse, respiratory rate, weight and blood pressure. Height will be measured at screening only. BP reading should be obtained 1 week after starting lenvatinib. Patients can either purchase a blood pressure cuff and the study team will train the subject on obtaining a BP at home, or it can be done by community health provider, as long as values are reported) and anti-hypertensives started if the systolic is ≥ 140 or diastolic is ≥ 90 or drug held per Section 5.2.2.6. The treating physician will prescribe anti-hypertensives.

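### Section 5.2.2.4 triggers blood pressure management on lenvatinib at systolic 150, but 5.2.2.6 and 7.1.2.4 start antihypertensives at systolic 140 (low severity)

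*Combined protocol and SAP*

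**What the plan says.** Three places in the protocol tell sites when to act on raised blood pressure during treatment.

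- **Section 5.2.2.4 (Management of AEs associated with lenvatinib)** has a bullet that sets a monitoring schedule and then its own trigger: "If a patient develops systolic BP ≥ 150 mmHg or diastolic BP ≥ 90 mmHg active management is indicated".
- **Section 5.2.2.6 (Management of Hypertension)** starts antihypertensives once a systolic value of 140 or more, or a diastolic value of 90 or more, has been confirmed on a second assessment at least half an hour later. It repeats the numbers for previously normotensive participants: "appropriate antihypertensive therapy should be started when systolic BP ≥ 140 mm Hg or diastolic BP ≥ 90 mm Hg". For participants already on antihypertensives it is softer: "treatment modification may be necessary if hypertension persists".
- **Section 7.1.2.4 (Vital Signs)** has "anti-hypertensives started if the systolic is ≥ 140 or diastolic is ≥ 90".

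Section 5.2.2.4 directs the reader to 5.2.2.6 for hypertension before its bullets begin. The flow chart in Section 6.1 does the same: "See Section 5.2.2.6 for management of hypertension and Section 7.1.2.4 for vital signs".

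Entry limits are set separately. Inclusion criterion 10 describes controlled pressure as "defined as a systolic BP ≤ 150 or a diastolic BP ≤ 90 mmHg at screening" and on the first treatment day. Exclusion criterion 24 rules out "Uncontrolled hypertension (systolic BP >150 mmHg or diastolic BP >90 mmHg) in spite of an optimized regimen of antihypertensive medication".

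**The concern.** One safety decision has two systolic thresholds. For a participant not already on antihypertensives, with a confirmed systolic of 145 and a diastolic of 80, Sections 5.2.2.6 and 7.1.2.4 say to start treatment. The 5.2.2.4 bullet does not yet call for action.

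The rule is likely to be used often. Section 4.2.2 reports treatment-related hypertension in 48% of 21 melanoma patients given this combination at these doses. That figure says nothing about how many readings fall between 140 and 149, but it shows that hypertension is a common event with this regimen.

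The setting also matters. Lenvatinib inhibits VEGF receptors, every participant has brain metastases, and 5.2.2.6 itself names intracerebral hemorrhage among the risk factors that bear on withholding the drug. The same section gives early control of blood pressure as the way to limit lenvatinib interruptions and dose reductions, and a later trigger works against that aim. The trial is multi-site, and the reading one week after starting lenvatinib may be taken at home or by a community provider. Sites and monitors therefore need a single number.

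**Working it through.** No sample size, error rate or event count is involved, so the check is a comparison of the rules. Let S be systolic and D diastolic pressure, in mm Hg.

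**Inputs**

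| Source | Trigger or limit |
|---|---|
| 5.2.2.4 (rule A) | S ≥ 150 or D ≥ 90 |
| 5.2.2.6 and 7.1.2.4 (rule B) | S ≥ 140 or D ≥ 90 |
| Entry limits (5.1.1 criterion 10, 5.1.2 criterion 24, 5.2.2.6) | S up to 150, D up to 90 |
| Next tier in 5.2.2.6 | S ≥ 160 or D ≥ 100 |

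**Step 1: size of the gap.** Systolic: 150 − 140 = 10 mm Hg. Diastolic: 90 − 90 = 0.

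**Step 2: where the rules differ.** If D ≥ 90, both trigger. If D < 90, A needs S ≥ 150 and B needs S ≥ 140. So B triggers without A exactly when 140 ≤ S < 150 and D < 90. A never triggers without B. Enumerating whole-number pairs (S from 80 to 220, D from 40 to 130) confirmed this: every pair on which the rules differ had S from 140 to 149 and D no higher than 89, and no pair triggered A alone.

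**Step 3: overlap with eligibility.** Every pair in that band has S ≤ 149 and D ≤ 89, so all of it lies inside the entry limits. A participant can take the first dose of lenvatinib already in the disputed range.

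**Step 4: could 150 be a deliberate second tier?** This is unlikely. A higher tier would be expected to raise the diastolic limit too, and it does not. The protocol has a separate next tier at 160/100. Active management is not defined as anything other than starting or adjusting antihypertensives. The pair 150/90 equals the entry limit, so it may have been carried over from there, but that is inference.

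**Step 5: after the correction.** With 150 changed to 140 in 5.2.2.4, rules A and B are identical and no pair of values is in dispute.

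The comparison covers the numeric thresholds only. Section 5.2.2.6 also requires confirmation by a second assessment, which 5.2.2.4 and 7.1.2.4 do not mention. That is a difference in procedure, separate from the threshold.

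**The case against.** The best counter-argument is that the protocol largely resolves this itself. Section 5.2.2.4 sends the reader to 5.2.2.6 before the bullet appears, the flow chart points to 5.2.2.6 and 7.1.2.4, and all of these lead to 140. Harm requires a site to use the bullet in isolation. The bullet also does not forbid treatment below 150. Any systolic reading that triggers it also exceeds 140, so a site that follows 5.2.2.6 complies with both. On this view the bullet is a loose summary line.

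Much of this stands, and it is why the severity is low. The referral makes 140 the likely intent, and the two rules can be obeyed together. It does not dispose of the point. The bullet gives a full monitoring schedule and an explicit trigger in one place, so it can be read as complete, and nothing says that the lower number governs.

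Two narrower objections are also fair. First, the 5.2.2.4 bullet speaks of pressure that develops on treatment, so the entry limits are context and not part of the conflict. The edit does not alter who may enrol. Second, because of the confirmation step in 5.2.2.6, the full procedures differ outside the 140 to 149 band as well. A single unconfirmed diastolic reading of 92, for example, meets 5.2.2.4 and 7.1.2.4 but not yet 5.2.2.6. The statement that the conflict is limited to that band therefore applies to the thresholds alone.

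**Conclusion.** The inconsistency is real and Section 5.2.2.4 is wrong as written. The systolic triggers differ by 10 mm Hg, and the difference affects only systolic 140 to 149 with diastolic below 90. It matters most for participants not already on antihypertensives; for those already treated, 5.2.2.6 leaves modification to judgement.

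The conclusion assumes that active management in 5.2.2.4 means the same kind of action as starting or adjusting antihypertensives, and that 140 is the intended threshold. The cross-references and the repeated use of 140 support the second assumption, but no text states it. No patient count can be derived.

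Severity is low. A site following 5.2.2.6 is unaffected, and so are the 160/100 rules, the primary endpoint, both Simon designs and the analysis.

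**What to change.** In Section 5.2.2.4, change the trigger to systolic 140 or above, or diastolic 90 or above, and add that the reading is to be confirmed and managed per Section 5.2.2.6. This aligns the bullet with 5.2.2.6 on both the threshold and the confirmation step.

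The cost is one number and one cross-reference. Visits, data collection, eligibility and analysis do not change.

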- Thyroid function, T3, T4 and TSH should be monitored before initiation of, and periodically throughout treatment with lenvatinib. Hypothyroidism should be treated according to standard medical practice to maintain euthyroid state.
- Monitor patients for clinical symptoms or signs of cardiac dysfunction as dose interruptions, adjustments, or discontinuation may be necessary.
- Gastrointestinal toxicity should be actively managed in order to reduce the risk of development of renal impairment or renal failure. Dose interruptions, adjustments, or discontinuation may be necessary.

5.2.2.5 Dose Reductions/ Interruptions for non-immune related Adverse Events attributed to Lenvatinib

Table 5 Dose Modification Guidelines for Lenvatinib-related Adverse Events

Treatment-Related Toxicity ^{a,b}	Management	Dose Adjustment
Grade 1 or Tolerable Grade 2	Continue treatment	No change
Intolerable Grade 2 ^c or Grade 3 ^d		
First occurrence	Interrupt lenvatinib until resolved to Grade 0-1, or tolerable Grade 2	Reduce lenvatinib dose to 14 mg once a day (1-level reduction)
Second occurrence (same toxicity or new toxicity)	Interrupt lenvatinib until resolved to Grade 0-1, or tolerable Grade 2	Reduce lenvatinib dose to 10 mg once a day (1-level reduction)
Third occurrence (same toxicity or new toxicity)	Interrupt lenvatinib until resolved to Grade 0-1, or tolerable Grade 2	Reduce lenvatinib dose to 8 mg orally once a day (1-level reduction)
Fourth occurrence (same toxicity or new toxicity)	Interrupt lenvatinib	Discuss with PI
Grade 4 ^e : Discontinue Study Treatment		

Note: For grading see CTCAE version 5.0. Collect all AE grades (ie, decreasing and increasing CTCAE grade).

a An interruption of study treatment for more than 28 days will require Sponsor's approval before treatment can be resumed.

b Initiate optimal medical management for nausea, vomiting, hypertension, hypothyroidism and/or diarrhea prior to any lenvatinib interruption or dose reduction.

c Applicable only to Grade 2 toxicities judged by the participant and/or physician to be intolerable.

d For asymptomatic laboratory abnormalities, such as Grade ≥ 3 elevations of amylase and lipase that are not considered clinically relevant by the investigator, continuation of treatment should be discussed with PI.

e Excluding laboratory abnormalities judged to be non-life-threatening, in which case manage as Grade 3.

Abbreviations: AE = adverse event; CTCAE = Common Terminology Criteria for Adverse Events

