5.2.2.9 Management of Hepatotoxicity

Liver function tests (alanine transaminase [ALT], aspartate transaminase [AST], bilirubin levels) should be conducted as detailed in the Study Flow Chart (Section 6.1) and as clinically indicated. If signs/symptoms indicating liver injury occur, instructions contained in Table 5 should be followed. Appropriate supportive care should be provided together with close monitoring. If hepatic failure occurs, the study drug must be discontinued. It might not be possible to determine whether LFT abnormalities are due to pembrolizumab or lenvatinib. Therefore, both drugs should be held and if no improvement is seen, corticosteroids should be initiated.

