5.2.2.14 Dose Modifications for Overlapping Toxicities

For overlapping toxicities where it is unclear if the event is related to one or both drugs, it is recommended to hold both drugs, and initiate management per Dose Modification Guidelines for Lenvatinib-Related Adverse Events. If toxicity does not improve within 1 to 2 days or worsens, management per Dose Modification Guidelines for Pembrolizumab-Related Adverse Events should be followed.

Participants who experience an unacceptable toxicity that is attributed to lenvatinib in the opinion of the investigator and the PI, may permanently discontinue lenvatinib, but may continue with pembrolizumab, upon resolution of toxicity to Grade 0 or 1 or baseline, until unacceptable toxicity or progression. Participants who discontinue pembrolizumab due to untoward toxicities may not continue on the trial receiving only lenvatinib.

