Pregnancy Test – Urine or Serum β-HCG	X	X	X	X	X	X	X	X	X	X	X			Performed within 10 days of C1D1 and prior to all subsequent scheduled visits. Every effort should be made to collect samples at the same time of day. LDH is only required at screening. Urine protein ≥2 requires 24-hour urine collection and D15 re-evaluation per Section 5.2.2.7. Pregnancy test for WOCP to be done within 72 hours days of C1D1.
PT/INR and aPTT	X													
CBC with Differential	X		X	X	X	X	X	X	X	X	X			
Comprehensive Serum Chemistry Panel	X		X	X	X	X	X	X	X	X	X			
Urinalysis	X		X	X	X	X	X	X	X	X	X			
T3, FT4 and TSH	X		X	X	X	X	X	X	X	X	X			
Efficacy Measurements														
Tumor Imaging (MRI brain ^e and CT Chest, Abdomen, Pelvis)	X		X		X				X	X		X	X	Prior scans performed within the screening period but before signing informed consent may be

														used. All imaging visits have a scheduling window of ± 7 d. Intracranial disease progression will be assessed by mRECIST 1.1. Extracranial disease will be assessed by RECIST 1.1. For participants who DC for reasons other than PD, imaging should be performed Q12W. Imaging at EOT is not required if the previous tumor imaging assessment was within 4 weeks prior to the EOT visit. Imaging of any anatomy that shows disease either at screening or in subsequent evaluations will be required and should be submitted.
Tumor Biopsies/Archival Tissue Collection/Correlative Studies														
Archival or Newly Obtained Tissue Collection	X													New tissue will be collected if the patient has a biopsy or resection for any reason while on study; a new consent will be obtained from the subject for use of part of the collected tissue for research.
Correlative Studies Blood Collection ^f		X	X	X			X			X				

a. Participants who continue treatment with lenvatinib beyond approximately 2 years (only if they experience clinical benefit until unacceptable toxicity or disease progression and upon Sponsor consultation and approval) will follow the same SOA except that thyroid labs beyond approximately 2 years will be performed per SOC or as clinically indicated.

b. If EOT visit occurs ~30 days from last dose of study treatment, a 30-day safety follow-up visit is not required. In this situation, all procedures required at the 30-day Safety Visit and EOT are performed once and entered into the EOT visit only. End of treatment will be defined as the date when the participant discontinues all trial treatments.

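### The 2-weekly liver tests that Section 5.2.2.4 sets for the first 2 months are missing from the flow chart that Section 5.2.2.9 sends sites to, which leaves one to three of the four dates uncovered

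*Combined protocol and SAP*

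**What the plan says.** Section 5.2.2.4, on lenvatinib adverse events, sets the frequency: "Liver function tests should be monitored before initiation of treatment, then every 2 weeks for the first 2 months and monthly thereafter during treatment". It also directs the reader to Section 5.2.2.9 for hepatotoxicity. There, ALT, AST and bilirubin "should be conducted as detailed in the Study Flow Chart (Section 6.1) and as clinically indicated".

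In the chart, these analytes belong to the comprehensive chemistry panel (Table 6, Section 7.1.3). The panel is marked at screening, not at cycle 1, then once at each cycle from cycle 2, at end of treatment and at safety follow-up. The timing note for the laboratory rows reads: "Performed within 10 days of C1D1 and prior to all subsequent scheduled visits".

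The chart does carry two other checks that fall between cycle visits. Footnote d adds blood-pressure readings 1 week after lenvatinib starts and then 2-weekly for 2 months. The laboratory note says that raised urine protein "requires 24-hour urine collection and D15 re-evaluation per Section 5.2.2.7". Footnote g refers schedulers to Table 6, which lists analytes and gives no liver-test frequency.

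**The concern.** The protocol gives two frequencies for one safety test during the first 2 months, and the hepatotoxicity section points to the sparser one. Section 5.2.2.4 gives blood pressure and liver tests parallel 2-weekly rules, and only the blood-pressure rule reached the chart. No reason is given for 3-weekly liver testing. This looks like an oversight, though the documents do not say so.

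What is at stake is when a rise is first found. Lenvatinib is taken daily, and each action rule starts from a known result:

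- Section 5.2.2.9: "If signs/symptoms indicating liver injury occur, instructions contained in Table 5 should be followed". For intolerable Grade 2 or Grade 3, Table 5 says: "Interrupt lenvatinib until resolved to Grade 0-1, or tolerable Grade 2". Tolerable Grade 2 continues unchanged.
- If the rise is immune-related, Table 3 withholds treatment from Grade 2, which is AST or ALT above 3.0 times the upper limit of normal when baseline is normal.
- If the cause cannot be assigned, Section 5.2.2.9 says: "Therefore, both drugs should be held and if no improvement is seen, corticosteroids should be initiated". For overlapping toxicities in general, Section 5.2.2.14 says "it is recommended to hold both drugs, and initiate management per Dose Modification Guidelines for Lenvatinib-Related Adverse Events".

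A rise without symptoms may give no clinical reason for an extra test, so a site that builds its visits from the chart could find it later than 5.2.2.4 intends.

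**Working it through.** This is calendar arithmetic; the plan states no figure to reproduce. Day 1 is the first dose (C1D1).

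**Inputs.** The 2-weekly interval is from Section 5.2.2.4. The 21-day cycle and the ±3-day visit window are from Sections 5.2.1 and 6.1. The allowance to draw up to 72 hours before dosing after cycle 1 is from Section 7.1.3.

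**Nominal dates, first 8 weeks.**
- Section 5.2.2.4: 1 + 14k gives days 15, 29, 43 and 57 (weeks 2, 4, 6 and 8), so four draws.
- Flow chart: 1 + 21k gives days 22 and 43 (weeks 3 and 6), so two draws. The next is day 64.
- Only day 43 is common, so three of the four dates are off the chart. Taking 2 months as 61 or 62 days leaves the nominal counts at four and two.
- Daily lenvatinib doses before the first test: 22 − 1 = 21, against 15 − 1 = 14.

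**With windows.** A chart draw can fall from 3 days + 72 hours before the planned dose day to 3 days after it. The documents do not say whether later cycles are counted from C1D1 (anchor A) or from the previous dose (anchor B).
- A: C2 days 16–25, C3 days 37–46, C4 days 58–67.
- B: C2 days 16–25, C3 days 34–49, C4 days 52–73.

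The documents also give no tolerance for the 2-weekly dates. The last column assumes ±3 days.

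| 2-weekly date | Exact day, A | Exact day, B | ±3 days assumed, A or B |
|---|---|---|---|
| Day 15 | outside | outside | 12–18 meets C2 |
| Day 29 | outside | outside | 26–32 meets none |
| Day 43 | inside C3 | inside C3 | 40–46 meets C3 |
| Day 57 | outside | inside C4 | 54–60 meets C4 |
| **Uncovered** | **3** | **2** | **1** |

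The last column is a best case: under A it needs the week 2 and week 8 draws to fall at the edge of a window. Day 29 fails throughout, because C2 ends on day 25 and C3 starts no earlier than day 34.

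**Spread of the first tests.** The first chart draw can fall on days 16 to 25, after 16 − 1 = 15 to 25 − 1 = 24 doses. The gap between the C2 and C3 draws is 37 − 25 = 12 to 46 − 16 = 30 days under A, and 21 − 3 − 3 = 15 to 21 + 3 + 3 = 27 days under B. The 2-weekly rule plans 14.

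All windows assume no cycle delay beyond ±3 days. A C2 delayed past its window could happen to cover week 4.

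**The case against.** The strongest reply is that the protocol does schedule these tests, in Section 5.2.2.4 itself. Section 7.1 describes the chart as a summary, so leaving a test off it does not cancel an instruction in the text. Sections 5.2.2.9 and 7.1 also allow unscheduled tests, so a site can satisfy everything by adding draws. That stands. A reader might infer that the 2-weekly tests are scheduled nowhere, or that the two texts cannot both be followed; the documents support neither reading. What remains is that 5.2.2.9 names the chart as the source, and permission to test when indicated does not plan a routine test.

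The consequence should not be overstated either. Table 5 footnote d leaves continuation to discussion with the PI for asymptomatic laboratory abnormalities not considered clinically relevant, and footnote e manages Grade 4 laboratory values judged non-life-threatening as Grade 3. Both leave room for judgement on the symptom-free rise at issue. Once a rise is known, Table 3 suggests considering weekly or more frequent tests, so only first detection is affected. Baseline and 3-weekly tests remain, and Section 7.1.3 requires results to be reviewed before each dose of trial treatment. The documents allow no estimate of harm.

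**Conclusion.** The inconsistency is real and narrow: it concerns safety monitoring in the first 2 months. Nominally the chart omits weeks 2, 4 and 8. The firm statement is that one to three of the four dates are uncovered, depending on the cycle anchor and on the tolerance allowed for the 2-weekly dates, neither of which is stated. Week 4 is uncovered on every reading without a cycle delay. A reader might take it that three checks are always lost; the windows do not support that.

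After month 2, 3-weekly draws satisfy the monthly rule. The primary endpoint and the Simon stopping rules are unaffected. It is worth correcting because these are early hepatotoxicity checks that the protocol itself calls for, and the correction is small.

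**What to change.** Add a flow-chart footnote modelled on footnote d: ALT, AST and bilirubin at weeks 2, 4, 6 and 8 after the first lenvatinib dose (days 15, 29, 43 and 57, each ±3 days); a cycle-day draw inside a window counts; local laboratories may be used, with results reported to the investigator. Have Section 5.2.2.9 refer to that footnote. Week 6 should be listed even though the C3 draw nominally covers it, because it would have no draw if C3 were delayed.

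The cost is one footnote, one cross-reference and about one to three extra local draws per patient who stays on treatment through week 8, or more if C3 is delayed. With no delay the total is at most about 62 × 3 = 186, and less if a cohort stops at stage 1 or patients leave early. At three extra draws a patient has five in the first 8 weeks (weeks 2, 3, 4, 6 and 8), because the C2 pre-dose draw stays.

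If the sponsor intends 3-weekly testing, Section 5.2.2.4 should be amended to say so and give the reason. That adds no draws but gives up the earlier checks. Either way, 5.2.2.4, 5.2.2.9 and the chart should state one schedule.
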